1.1 Study design

This is a randomized, phase III, double blind, placebo controlled, international study to determine the efficacy and safety of treatment with fulvestrant with ribociclib versus fulvestrant with placebo in men and postmenopausal women with HR+, HER2-negative advanced breast cancer. This study will consist of 4 phases: screening (up to 28 days), randomized treatment, post-treatment efficacy follow-up, and post-treatment survival follow-up.

Approximately 660 patients will be randomly assigned to one of the following treatment arms in a 2:1 ratio.

- Experimental arm: fulvestrant (500 mg intramuscular [as two 5 mL injections] on Cycle 1 Days 1 and 15 (C1D1 and C1D15), and on CnD1 thereafter) + ribociclib (600 mg by mouth once daily for three weeks followed by one week break, in a 28-day cycle)
OR
- Control arm: fulvestrant (500 mg intramuscular [as two 5 mL injections] on Cycle 1 Days 1 and 15 (C1D1 and C1D15), and on CnD1 thereafter) + ribociclib placebo (by mouth once daily for three weeks followed by one week break, in a 28-day cycle)

Randomization will be stratified by the following factors:

1. Lung or liver metastases: (yes vs no)
2. Previous endocrine therapy (A vs B) according to the following definition:
 - A) Patients treatment naïve in the metastatic/advanced disease setting:
 - i- whose disease relapsed >12 months after completion of (neo)adjuvant endocrine therapy with no subsequent treatment for advanced/metastatic disease,
OR
 - ii- with de-novo advanced/metastatic disease (no prior exposure to endocrine therapy).
 - B) Patients who received up to 1 line of treatment for metastatic/advanced disease:
 - i- whose disease relapsed on or within 12 months from completion of (neo) adjuvant endocrine therapy, with no subsequent treatment for advanced/metastatic disease,

OR

ii- whose disease relapsed > 12 months from completion of (neo) adjuvant endocrine therapy, and progressed on or after subsequent endocrine treatment for advanced/metastatic disease,

[figure not shown]
OR

iii- with advanced/metastatic disease at the time of diagnosis that progressed on or after endocrine therapy for advanced/metastatic disease with no prior (neo) adjuvant treatment for early disease.

Following the statistically significant PFS and OS benefit, with protocol amendment 4, study participants were unblinded, with an opportunity for those patients still on study treatment in the placebo combination arm to cross-over to the LEE011 combination arm. Crossover was optional and was conducted only upon documented consent of the study patient.

The study design is summarized in [Figure 1-1](#).

Figure 1-1 Study Design

[figure not shown]

1.2 Objectives

The study objectives and corresponding endpoints as specified in the protocol are provided in [Table 1-1](#). PFS, as assessed by the local radiologists/investigators and using RECIST 1.1 criteria is the primary endpoint. Overall survival is a secondary endpoint. Both PFS and OS have been tested statistically significant and results have been summarized by previous study reports.

Table 1-1 Study objectives

Objective	Endpoint
Primary	
To compare PFS between ribociclib in combination with fulvestrant to placebo in combination with fulvestrant among men and postmenopausal women with HR+, HER2-negative advanced breast cancer who received no or only one prior endocrine treatment for advanced disease	PFS based on local radiology assessments and using RECIST 1.1 criteria
Secondary	
To compare the two treatment arms with respect to overall survival.	Overall survival
To evaluate the two treatment arms with respect to overall response rate, clinical benefit rate, time to response and duration of response.	ORR as defined by RECIST 1.1. CBR, defined as percentage of patients with CR, PR or SD lasting 24 weeks or longer, TTR, DOR per RECIST 1.1
To evaluate the two treatment arms with respect to time to deterioration of ECOG performance status.	Time to definitive deterioration of ECOG performance status from baseline
To evaluate the safety and tolerability of ribociclib in combination with fulvestrant.	Frequency/severity of AEs, laboratory abnormalities
To evaluate patient reported outcomes for health-related quality of life in the two treatment arms.	Time to 10% deterioration in the global health status/QOL scale score of the EORTC QLQ-C30 Change from baseline in the global health status/QOL scale score of the EORTC QLQ-C30
To characterize the pharmacokinetics (PK) of ribociclib (and relevant metabolites such as LEQ803) when given in combination with fulvestrant.	Concentration by time point for ribociclib (and relevant metabolites such as LEQ803)

Objective	Endpoint

2 Definitions and general methodology

2.1 Definitions

2.1.1 Study drug and study treatment

Study drug is defined as ribociclib or matching placebo.

Study treatment is defined as ribociclib + fulvestrant, or matching placebo + fulvestrant.

Cross-over open-label ribociclib treatment will refer to ribociclib drug administered to patients randomized to placebo plus fulvestrant arm who subsequently cross-over to ribociclib plus fulvestrant (cross-over period).

Cross-over open-label ribociclib plus fulvestrant treatment will refer to the combination of drugs ribociclib plus fulvestrant administered during the cross-over period.

2.1.2 Date of first administration of study drug

The date of first administration of study drug is defined as the first date when a nonzero dose of study drug is administered and recorded on the dose administration DAR CRF. The date of first administration of study drug will also be referred to as start of study drug. Similar definitions apply for the other components of study treatment.

For analyses related to the cross-over period, date of first administration of cross-over open-label ribociclib treatment is defined as the first date when a non-zero dose of cross-over open-label ribociclib treatment is administered and recorded on the DAR CRF, after the date of cross-over recorded on the cross-over Details CRF.

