Study days			-28 to -1	-7 to -1	1	15	1	15	1	1	Within 15 days from last dose	Last dose + 30 days	Every 8 weeks (if applicable)		Every 12 weeks
Patient Quality of life questionnaires															
EORTC QLQ-C30	D	7.2.6.1	x		NA after protocol amendment 4.										
EQ-5D-5L	D	7.2.6.2	x		NA after protocol amendment 4.										
BPI-SF	D	7.2.6.3	x		NA after protocol amendment 4.										
Study Drug administration															
fulvestrant	D				x	x	x		x	x					
ribociclib (LEE011) / placebo	D				Day 1 to Day 21 daily, Day 22 to Day 28 off										
Discontinuation															
IRT – Discontinuation	S	7.1.3									x				
Antineoplastic therapies since discontinuation of study treatment	D	7.1.6									x	x	x		x
Survival follow-up	D	7.1.7													x

**Table 7-1b Visit evaluation schedule – Cross over treatment phase for patients who cross over from placebo to LEE011 after protocol amendment 4.**

Visit name	Category	Reference to Protocol Section	Treatment Phase - only applies to cross-over patients for cross over treatment cycles						Post treatment follow-up phase			Survival phase	
			Cross over Cycle 1		Cross over Cycle 2		Cross over Cycles 3 to 6	All subsequent Cross over cycles	End of study treatment (EOT)	Safety follow-up	Efficacy follow-up	End of post-treatment follow-up	Survival follow-up
Study days			1	15	1	15	1	1	Within 15 days from last dose	Last dose + 30 days	Every 8 weeks (if applicable)		Every 12 weeks
Dispensing													
IRT – cross over registration			x										
IRT – study drug administration			x		x		x	x	x				
Physical Examination													
Physical examination	S	7.2.2.1	x		x		x	Every 3 rd cycle	x				
Performance status (ECOG)	D	7.2.2.4	x		x		x	Every 3 rd cycle	x				
Weight	D	7.2.2.3	X		x		x	As clinically indicated	x				
Vital signs	D	7.2.2.2	x		x		x	Every 3 rd cycle	x				
Laboratory assessments													

Visit name	Category	Reference to Protocol Section	Treatment Phase - only applies to cross-over patients for cross over treatment cycles						Post treatment follow-up phase			Survival phase		
			Cross over Cycle 1		Cross over Cycle 2		Cross over Cycles 3 to 6	All subsequent Cross over cycles	End of study treatment (EOT)	Safety follow-up	Efficacy follow-up	End of post-treatment follow-up	Survival follow-up	
Study days			1	15	1	15	1	1	Within 15 days from last dose	Last dose + 30 days	Every 8 weeks (if applicable)		Every 12 weeks	

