2.1.3 Date of last administration of study drug

The date of last administration of study drug is defined as the last date when a nonzero dose of study drug is administered and recorded on the DAR CRF. Similar definitions apply for the other components of study treatment.

For analyses related to the cross-over period, date of last administration of cross-over open-label ribociclib treatment is defined as the last date when a non-zero dose of cross-over open-label ribociclib treatment is administered and recorded on the DAR CRF, after the date of crossover recorded on the cross-over Details CRF.

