2.1.4 Date of first administration of study treatment

The date of first administration of study treatment is defined as the first date when a nonzero dose of any component of study treatment is administered and recorded on the DAR CRF. The

date of first administration of study treatment will also be referred to as the start of study treatment.

For analyses related to the cross-over period, date of first administration of cross-over open-label ribociclib plus fulvestrant treatment is equal to the date of first administration of cross-over open-label ribociclib treatment.

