2.1.7 Baseline

For safety evaluations (e.g., laboratory assessments and ECG), the last available assessment before or at date of start of study treatment will be used as the ‘baseline’ assessment. Assessments specified to be collected post-dose on the first date of treatment are not considered as baseline values.

If patients have no value as defined above, the baseline results will be considered missing.

For cross-over analyses, the last available assessment before or on the date of first dose of cross-over open-label ribociclib treatment will be used as the ‘baseline’ assessment.

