2.1.8 On-treatment assessment/event

Safety summaries and selected summaries of deaths will summarize only on-treatment assessments/events.

Double-blind on-treatment period:

An on-treatment assessment/event is defined as any assessment/event in the following time interval:

[date of first administration of study treatment, the earliest between the date of last administration of study treatment + 30 days and the date of first administration of cross-over open-label ribociclib plus fulvestrant treatment – 1 day], i.e., including the lower and upper limits.

The double-blind on-treatment period is the **default** on-treatment period used in the analyses unless specified otherwise.

Cross-over on-treatment period:

An on-treatment assessment/event is defined as any assessment/event in the following time interval: [date of first administration of the cross-over open-label ribociclib plus fulvestrant treatment, date of last administration of the cross-over open-label ribociclib plus fulvestrant treatment + 30 days], i.e., including the lower and upper limits.

(Note: However, the calculation of study treatment duration will use different rules as specified in [Section 3.5.1](#)).

An AE started in the screening phase and ongoing in the on-treatment phase will not be considered as an on-treatment AE unless it has worsened.

If the last date of study treatment is missing, any assessment/event occurring after the start of study treatment will be considered as on-treatment.

Data listings will include all assessments/events, flagging those which are not on-treatment.

Note: The date of first administration of study treatment and the date of last administration of study treatment are defined in [Sections 2.1.4](#) and [2.1.5](#), respectively.

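### The final SAP's strict *after* rule can drop a cross-over patient's first ribociclib day, because the cross-over date it depends on is not defined

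*SAP*

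**What the plan says.** The SAP for the final study report defines the first cross-over ribociclib date in 2.1.2 as the earliest date of a non-zero open-label dose "after the date of cross-over recorded on the cross-over Details CRF". Section 2.1.3 applies the same condition to the last dose: "after the date of crossover recorded on the cross-over Details CRF".

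Other definitions take this date over:

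- 2.1.4: the start of the cross-over combination "is equal to the date of first administration of cross-over open-label ribociclib treatment".
- 2.1.6: it is the reference date for the cross-over study day.
- 2.1.7: the cross-over baseline is "the last available assessment before or on the date of first dose" of open-label ribociclib.
- 2.1.8: the double-blind on-treatment period ends at the earlier of last study treatment plus 30 days and the "date of first administration of cross-over open-label ribociclib plus fulvestrant treatment – 1 day". This double-blind window is the default "on-treatment period used in the analyses unless specified otherwise". The cross-over on-treatment period opens on the same start date.
- 3.5.1: cross-over exposure is counted from it.

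In the protocol, Table 7-1b marks "IRT – cross over registration" under cross-over Cycle 1 Day 1, and ribociclib is given daily from Day 1 to Day 21 of each cycle. Protocol 10.1.5 starts the cross-over phase at the first LEE011 dose after cross-over and sets no condition relative to a CRF date.

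**The concern.** As written, *after* excludes the date itself. The SAP writes inclusive limits elsewhere when it means them: 2.1.6, 2.1.7 and 3.7.1.3 all include the boundary day explicitly. A programmer therefore has no reason to read 2.1.2 as inclusive.

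If the CRF date is the day on which the patient was registered for cross-over and took the first capsule, the true first dose fails the test. The cut between placebo and ribociclib data then falls one day late. Ribociclib-exposed time is reported in the placebo column of the default safety tables, and the cross-over outputs start from a wrong origin. The direction is known: events move from ribociclib to placebo.

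**Working it through.** The documents state no figure to reproduce, so this is a check of dates. Call cross-over Cycle 1 Day 1 day 1 and the day before it day 0. The inputs are ribociclib doses on days 1 to 21 and 29 to 49 (Table 7-1b), the dose rule in SAP 2.1.2, and the period end in SAP 2.1.8, which is min(last study treatment + 30, derived start − 1).

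**Case A: CRF date = day 1, rule read literally.**

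- Derived start: first dose date later than day 1 = day 2.
- Double-blind end: min(last study treatment + 30, 2 − 1) = day 1. The 30-day limit does not bind. If the last earlier dose was fulvestrant on day 1 − 28 = −27, the limit is −27 + 30 = 3. If it was placebo on day 21 of the previous cycle (day −7), the limit is −7 + 30 = 23. Both exceed 1.
- So one ribociclib day, day 1, lies in the double-blind placebo period.
- Study day (2.1.6): day 1 precedes the reference date and becomes 1 − 2 = −1; day 15 becomes 15 − 2 + 1 = 14.
- Ribociclib exposure over the first dosing block: 21 − 2 + 1 = 20 days instead of 21 − 1 + 1 = 21.
- Baseline: any assessment up to and including day 2 qualifies, so one taken on day 2, after the day 1 dose, could be used.
- A patient whose only open-label dose was on day 1 would have no derived first or last dose. That patient would still belong to the cross-over analysis set, because SAP 2.3.3 requires one open-label dose without a date condition.

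**Case B: CRF date 1 to 3 days before the first dose.** The first dose date later than the CRF date is day 1. The double-blind period ends on day 0. Nothing is misassigned.

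**Case C: *on or after*, with the CRF date on day 1 or 1 to 3 days earlier.** The derived start is day 1 and the double-blind period ends on day 0.

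**Case D: CRF date = day 1, rule applied to the start dates of dosing records, one record per 21-day block.** The first record starting later than day 1 begins on day 29. The double-blind period then ends on day 28 if treatment from day 1 onward counts as study treatment. If only pre-cross-over doses count, it ends on day 3 (fulvestrant last) or day 23 (placebo last). The SAP does not prescribe this implementation.

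**The case against.** The strongest reply is that the CRF field is not the IRT registration. The IRT is a separate system (protocol 6.3.2). Cross-over requires documented consent (4.1.2), and protocol 7.1 gives instructions for patients who elect to cross over at their next scheduled visit, so election can precede the first dose. If the Cross-over Details page holds that earlier date, the strict rule finds the right dose (Case B). This stands: a reader might infer from Table 7-1b that the CRF date must be Day 1, but the documents do not establish that. They do not rule it out either, and leaving the date undefined is itself a gap.

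A reader might also infer that the whole first cycle, including the neutropenia that protocol 1.2.1.2.1 places by Day 15 and the QT changes it places by Day 8, would be reported under placebo. The documents do not support this. SAP 2.1.2 refers to the first date on which a dose is administered, which gives Day 2 under daily dosing. A longer shift needs Case D. Dosing records do carry start and end dates (SAP 2.1.9), so Case D is possible, but the SAP does not state it, and the 30-day limit could shorten it.

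The baseline consequence is also narrow. The scheduled Day 1 ECG is pre-dose, and Table 7-5b has no further scheduled ECG until Day 15. A Day 2 baseline therefore requires an unscheduled or delayed assessment. SAP 2.1.7 excludes assessments specified as post-dose on the first treatment date, but its cross-over sentence does not repeat this, and the exclusion would not reach an unscheduled Day 2 value.

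Finally, much of the cross-over safety output is listings. That limits the effect without removing it: the default by-arm safety tables, the disclosure tables (3.7.1.6) and the key safety analyses on the cross-over set (3.7) all depend on these windows.

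**Conclusion.** The point holds conditionally and is minor. If the CRF cross-over date is the registration or first-dose day and 2.1.2 is followed literally, each cross-over patient's start moves from Day 1 to Day 2. The consequences are Day 1-onset events in the placebo period, study days one too low, one lost exposure day, and a possible on-drug baseline. If the CRF date is earlier, there is no error. A shift of up to a full cycle belongs only to a record-start-date implementation that the SAP does not describe, and should not be read into the plan.

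The documents do not give the number of cross-over patients, so the change in placebo-arm event rates cannot be sized. PFS and OS were already tested and reported (SAP 1.2), and this rule does not affect them.

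**What to change.** 1. In final SAP 2.1.2 and 2.1.3, change the condition to *on or after* the date of cross-over, or define both dates from the open-label ribociclib doses themselves, in line with protocol 10.1.5. The inclusive wording is safe whether the CRF date is the dosing day or earlier: SAP 2.1.1 already limits open-label ribociclib to drug given to placebo-randomised patients who crossed over, so no placebo dose can enter.
2. State which event the date on the Cross-over Details CRF records: consent, registration or first dose.
3. In 2.1.7, take the cross-over baseline from the last assessment before the first open-label ribociclib dose.

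The cost is a short SAP edit and a matching check of the programming specification, best made before programming. No new data are needed and patients are not affected.

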2.1.3 Date of last administration of study drug

The date of last administration of study drug is defined as the last date when a nonzero dose of study drug is administered and recorded on the DAR CRF. Similar definitions apply for the other components of study treatment.

For analyses related to the cross-over period, date of last administration of cross-over open-label ribociclib treatment is defined as the last date when a non-zero dose of cross-over open-label ribociclib treatment is administered and recorded on the DAR CRF, after the date of crossover recorded on the cross-over Details CRF.

2.1.4 Date of first administration of study treatment

The date of first administration of study treatment is defined as the first date when a nonzero dose of any component of study treatment is administered and recorded on the DAR CRF. The

date of first administration of study treatment will also be referred to as the start of study treatment.

For analyses related to the cross-over period, date of first administration of cross-over open-label ribociclib plus fulvestrant treatment is equal to the date of first administration of cross-over open-label ribociclib treatment.

2.1.5 Date of last administration of study treatment

The date of last administration of study treatment is defined as the last date when a nonzero dose of any component of study treatment was administered and recorded on the DAR CRF.

For analyses related to the cross-over period, date of last administration of cross-over open-label ribociclib plus fulvestrant treatment is defined as the last date when a non-zero dose of any component of the cross-over open-label ribociclib plus fulvestrant treatment was administered and recorded on the DAR CRF during the cross-over period.

2.1.6 Study day

The study day will be calculated as:

- The date of the event (visit date, onset date of an event, assessment date etc.) – reference start date + 1 if event is on or after the reference start date;
- The date of the event (visit date, onset date of an event, assessment date etc.) – reference start date if event precedes the reference start date.

The reference start date for safety assessments (e.g., adverse event onset, laboratory abnormality occurrence, vital sign measurement, dose interruption etc.) is the start of study treatment. (Note: if an adverse event starts before the start of study treatment the study day displayed on the listing will be negative).

The study day will be displayed in data listings.

For analyses related to the cross-over period, study day is defined as above, with the reference date being the date of first administration of cross-over open-label ribociclib treatment.

2.1.7 Baseline

For safety evaluations (e.g., laboratory assessments and ECG), the last available assessment before or at date of start of study treatment will be used as the ‘baseline’ assessment. Assessments specified to be collected post-dose on the first date of treatment are not considered as baseline values.

If patients have no value as defined above, the baseline results will be considered missing.

For cross-over analyses, the last available assessment before or on the date of first dose of cross-over open-label ribociclib treatment will be used as the ‘baseline’ assessment.

2.1.8 On-treatment assessment/event

Safety summaries and selected summaries of deaths will summarize only on-treatment assessments/events.

Double-blind on-treatment period:

An on-treatment assessment/event is defined as any assessment/event in the following time interval:

[date of first administration of study treatment, the earliest between the date of last administration of study treatment + 30 days and the date of first administration of cross-over open-label ribociclib plus fulvestrant treatment – 1 day], i.e., including the lower and upper limits.

The double-blind on-treatment period is the **default** on-treatment period used in the analyses unless specified otherwise.

Cross-over on-treatment period:

An on-treatment assessment/event is defined as any assessment/event in the following time interval: [date of first administration of the cross-over open-label ribociclib plus fulvestrant treatment, date of last administration of the cross-over open-label ribociclib plus fulvestrant treatment + 30 days], i.e., including the lower and upper limits.

(Note: However, the calculation of study treatment duration will use different rules as specified in [Section 3.5.1](#)).

An AE started in the screening phase and ongoing in the on-treatment phase will not be considered as an on-treatment AE unless it has worsened.

If the last date of study treatment is missing, any assessment/event occurring after the start of study treatment will be considered as on-treatment.

Data listings will include all assessments/events, flagging those which are not on-treatment.

Note: The date of first administration of study treatment and the date of last administration of study treatment are defined in [Sections 2.1.4](#) and [2.1.5](#), respectively.

